8.2 Laboratory Assessments Related to SLE Disease Activity

The following laboratory tests will be performed according to the schedule in [Section 1.3](#) to gather more information about SLE disease activity: Coomb's test (direct); serum complement (C3, C4); quantitative immunoglobulins (IgG, IgA, IgM); anti-dsDNA; anti-Sm; ANA; anti-Ro (SSA); anti-La (SSB); anti-ribonucleoprotein (RNP); T cells, B cells, and natural killer cells (TBNK); and high-sensitivity C-reactive protein. Laboratory assessments that are used in some efficacy assessments (eg, BILAG and SLEDAI-2K), such as complete blood count and renal function tests, are also used for safety assessments and are described in [Section 8.5.3](#). Samples for confirmation of hemolysis (using haptoglobin and reticulocyte count) for the BILAG will be drawn at assessment visits and stored at the central laboratory; the samples will only be analyzed if there is clinical suspicion on the part of the investigator.

8.3 Adverse Events

Adverse events will be reported by the subject (or, when appropriate, by a caregiver, surrogate, or the subject's legally authorized representative).

The investigator and any designees are responsible for detecting, documenting, and reporting events that meet the definition of an AE or serious adverse event (SAE) and remain responsible for following up AEs that are serious, considered related to the study treatment or the study, or that caused the subject to discontinue before completing the study.

The definitions of an AE or SAE can be found in [APPENDIX 3](#).

Contacts for SAE reporting are specified in [Appendix 3](#).

The event (term), along with its start and stop dates, maximum intensity (mild, moderate, or severe), seriousness (yes/no), relationship to the IP (yes/no), action taken with regard to the IP, and outcome will be recorded in the eCRF.

8.3.1 Adverse Events of Interest

Adverse events of interest (AEIs) are AEs for a particular product or class of products that a Sponsor may wish to monitor carefully. Adverse events of interest may be serious or nonserious. Such events may require further investigation to better characterize and understand them. In the BMS-986165 clinical development program, certain skin-related AEs (eg, acne) and infection AEs have been identified as potential AEIs; however, there has been no definitive assessment on the causal relationship between these events and treatment with BMS-986165. Therefore, additional information about certain AEs may be collected on the eCRF in order to better characterize and understand them.

8.3.2 Time Period and Frequency for Collecting AE and SAE Information

The collection of nonserious AE information should begin at initiation of study treatment and continue until the last follow-up visit, at the timepoints specified in the Schedules of Activities ([Section 1.3](#)).

The Reference Safety Information in Sections 5.6.1 and 5.6.2 of the IB should be used to determine the expectedness of SAEs for expedited reporting. Following the subject's written consent to

participate in the study, all SAEs, whether related or not related to study treatment, must be collected, including those thought to be associated with protocol-specified procedures.

All SAEs that occur from the time the informed consent form (ICF) is signed through 30 days after the final dose of the study treatment must be reported to [REDACTED] Drug Safety. After that time, only SAEs deemed by the investigator to be related to the study treatment or a study procedure should be reported.

- The investigator must report any SAE that occurs after these time periods and that is believed to be related to study treatment or protocol-specified procedure. Medical occurrences that begin before the start of study treatment but after obtaining informed consent will be recorded on the appropriate section of the eCRF.
- All SAEs will be recorded and reported to Sponsor or designee within 24 hours, as indicated in [APPENDIX 3](#).
- The investigator will submit any updated SAE data to the Sponsor within 24 hours of this being available.

Investigators are not obligated to actively seek AEs or SAEs in former study subjects. However, if the investigator learns of any SAE, including a death, at any time after a subject has been discharged from the study, and he/she considers the event reasonably related to the study treatment or study participation, the investigator must promptly notify the Sponsor.

The method of evaluating and assessing causality of AEs and SAEs and the procedures for completing and reporting/transmitting SAE reports are provided in [APPENDIX 3](#).

8.3.3 Method of Detecting AEs and SAEs

Adverse events can be spontaneously reported or elicited during open-ended questioning, examination, or evaluation of a subject. To prevent reporting bias, subjects should not be questioned regarding the specific occurrence of one or more AEs. Adverse events will be reported by the subject (or, when appropriate, by a caregiver, surrogate, or the subject's legally authorized representative). Nonserious SLE-related AEs will be collected only on the disease assessment instruments and not reported as AEs.

All AEs and SAEs that arise in the study will be reported and investigated. However, because of the characteristics of the disease under study and of BMS-986165 itself, subjects will be more closely monitored for signs of infection and for treatment-emergent rash ([Section 8.3.9](#)).

8.3.4 Follow-up of AEs and SAEs

- Nonserious AEs should be followed to resolution or stabilization, or reported as SAEs if they become serious (see [APPENDIX 3](#)).
- Follow-up is also required for nonserious AEs that cause interruption or discontinuation of study treatment and for those present at the end of study treatment as appropriate.
- All identified nonserious AEs must be recorded and described on the nonserious AE page of the CRF. Completion of supplemental CRFs may be requested for certain AEs, such as

skin reactions and infections, and/or laboratory abnormalities that are reported/identified during the course of the study.

After the initial AE/SAE report, the investigator is required to proactively follow each subject at subsequent visits/contacts. All SAEs will be followed until resolution, until the condition stabilizes, until the event is otherwise explained, or until the subject is lost to follow-up (as defined in [Section 7.4](#)).

Further information on follow-up procedures is given in [APPENDIX 3](#).

8.3.5 Regulatory Reporting Requirements for SAEs

- Prompt notification by the investigator to the Sponsor of SAEs is essential so that legal obligations and ethical responsibilities towards the safety of subjects and the safety of a product under clinical investigation are met.
- An investigator who receives an investigator safety report describing SAEs or other specific safety information (eg, summary or listing of SAEs) from the Sponsor will file it along with the IB and will notify the institutional review board (IRB)/independent ethics committee (IEC), if appropriate according to local requirements.

The Sponsor or designee will be reporting AEs to regulatory authorities and ethics committees according to local applicable laws including European Directive 2001/20/EC and Food and Drug Administration Code of Federal Regulations 21 CFR Parts 312 and 320. Suspected, unexpected serious adverse reactions are a subset of SAEs and will be reported to the appropriate regulatory authorities and investigators following local and global guidelines and requirements.

8.3.6 Pregnancy

If, following initiation of the study treatment, it is subsequently discovered that a subject is pregnant or may have been pregnant at the time of study exposure, including during at least 5 half-lives after product administration, the investigator must immediately notify [REDACTED] Drug Safety of this event and complete and forward a Pregnancy Surveillance Form to [REDACTED] Drug Safety within 24 hours of awareness of the event and in accordance with SAE reporting procedures described in [APPENDIX 3](#).

In most cases, the study treatment will be permanently discontinued in an appropriate manner (eg, dose tapering if necessary for subject safety).

Any pregnancy that occurs in a female partner of a male study subject should be reported to [REDACTED] Drug Safety. For the Sponsor or designee to collect any pregnancy surveillance information from the female partner, the female partner must sign an ICF for disclosure of this information. Information on this pregnancy will be collected on the Pregnancy Surveillance Form.

Protocol-required procedures for study discontinuation and follow-up must be performed on subjects who become pregnant.

Follow-up information regarding the course of the pregnancy, including perinatal and neonatal outcome and, where applicable, offspring information must be reported on the Pregnancy Surveillance Form.

8.3.7 Laboratory Test Result Abnormalities

The following laboratory test result abnormalities should be captured on the nonserious AE CRF page or electronic SAE Report Form, as appropriate. Paper forms are only intended as a back-up option when the electronic system is not functioning.

- Any laboratory test result that is clinically significant or meets the definition of an SAE
- Any laboratory test result abnormality that required the subject to have study treatment discontinued or interrupted
- Any laboratory test result abnormality that required the subject to receive specific corrective therapy

It is expected that wherever possible, the clinical rather than laboratory term would be used by the reporting investigator (eg, anemia versus low hemoglobin value).

8.3.8 Potential Drug-Induced Liver Injury

Wherever possible, timely confirmation of initial liver-related laboratory abnormalities should occur prior to the reporting of a potential DILI event. All occurrences of potential DILIs, meeting the defined criteria, must be reported as SAEs (see [APPENDIX 3](#) for reporting details).

Potential DILI is defined by presence of all of the following characteristics:

- ALT or AST elevation $> 3 \times$ ULN
- total bilirubin $> 2 \times$ ULN, without initial findings of cholestasis (elevated serum alkaline phosphatase)
- no other immediately apparent possible causes of AST or ALT elevation and hyperbilirubinemia, including, but not limited to, viral hepatitis, preexisting chronic or acute liver disease, or the administration of other drug(s) known to be hepatotoxic

8.3.9 Other Safety Considerations

Any significant worsening noted during interim or final physical examinations, ECG, X-ray filming, any other potential safety assessment required or not required by protocol should also be recorded as a nonserious or serious AE, as appropriate, and reported accordingly.

8.4 Overdose

For this study, any dose of blinded study treatment that is more than 2-days' worth of study treatment within a 24-hour time period will be considered an overdose.

In the event of an overdose the investigator should:

1. Contact the [REDACTED] medical monitor immediately.
2. Closely monitor the subject for AEs/SAEs and laboratory abnormalities until BMS-986165 can no longer be detected systemically (at least 3 days).
3. Document the quantity of the excess dose as well as the duration of the overdosing in the eCRF.

Decisions regarding dose interruptions or modifications will be made by the investigator in consultation with the [REDACTED] medical monitor based on the clinical evaluation of the subject.

8.5 Safety

Planned timepoints for all safety assessments are listed in the Schedules of Activities (Section 1.3). All urgent safety concerns must be discussed with the Sponsor immediately upon occurrence or awareness to determine if the subject should continue or discontinue treatment.

Safety evaluations that will be performed in addition to AE monitoring are physical examinations (PE; Section 8.5.1), TB screening (Section 8.5.2), vital signs, ECGs, concomitant medication use, and laboratory tests (Section 8.5.3).

8.5.1 Physical Examinations

Schedules for PEs are provided in Section 1.3. Complete and/or targeted PEs may be performed by a Doctor of Medicine (MD), or someone who is authorized to perform the examinations by training and has been delegated this task by the principal investigator. While the targeted examination may not be as comprehensive as the initial full examination, key aspects should evaluate important body systems as clinically indicated. These body systems can include lymph nodes, liver, spleen, and breast at the discretion of the examiner. A targeted examination may note any changes in the subject's condition (body systems) since the last assessment and does not preclude examination of any of the other body systems as clinically indicated. Every effort should be made to ensure the same evaluator will complete the examination for each subject at all visits throughout the study. Documentation of who performed the examination is to be recorded in source notes.

8.5.2 Tuberculosis Screening and Chest X-ray

A chest X-ray and PE are part of the process to assess a subject's eligibility as defined in Section 5.2, Exclusion Criterion 4a, and outlined in Section 1.3. A chest X-ray at the screening visit is required if not already performed within 6 months of obtaining written informed consent.

In addition to a complete PE and medical history to evaluate exposure to TB, all subjects will have a screening test, an IGRA (eg, T-spot[®] or QuantiFERON[®]), preferably performed centrally. If unable to obtain central laboratory results (eg, repeated test due to indeterminate result), an IGRA test could be obtained locally, after consultation with the [REDACTED] medical monitor.

8.5.3 Clinical Safety Laboratory Assessments

A central laboratory will perform assessments of safety laboratory assessments (except pregnancy tests) and provide reference ranges and laboratory reports. Investigators must document their review of each laboratory safety report. Any laboratory test result that the investigator considers clinically relevant is to be recorded on the appropriate AE page of the eCRF (Section 8.3.7). Results of clinical laboratory tests performed during screening must be available prior to randomization. Additional safety assessments may be performed at local laboratories at the investigator's discretion. The laboratory parameters to be assessed are as follows:

- Hematology: hemoglobin, hematocrit, total leukocyte count (including differential), platelet count, RBC count, and manual differential (separate smear)

- Chemistry: AST, ALT, gamma glutamyltransferase, total bilirubin, direct bilirubin, alkaline phosphatase, lactate dehydrogenase, creatinine, blood urea nitrogen, uric acid, fasting glucose, total protein, albumin, sodium, potassium, chloride, calcium, phosphorus, magnesium, creatine kinase, creatinine clearance (screening only)
- Coagulation: prothrombin time, INR, and either partial thromboplastin time or activated partial thromboplastin time
- TSH (screening only)
- Tests performed after a ≥ 10 -hour fast: lipid panel (total cholesterol, high-density lipoprotein cholesterol, low-density lipoprotein cholesterol, and triglycerides), plasma glucose
- Urinalysis: protein, glucose, blood, leukocyte esterase, specific gravity, pH; microscopic examination of the sediment if blood, protein, or leukocyte esterase are positive on dipstick; spot urine will be assessed for urine protein and urine creatinine
- Serology to be performed at screening: hepatitis C antibody, HBsAg, anti-HBc, HIV-1 and HIV-2 antibody, TB (screening only)

In addition, urine pregnancy testing will be performed for WOCBP, and follicle-stimulating hormone will be measured to confirm postmenopausal status (as applicable; at screening only).

8.5.4 Imaging Safety Assessment

Not applicable.

8.6 Pharmacokinetics

The PK of BMS-986165 and metabolites (if applicable) will be derived from plasma concentration versus time.

Plasma samples will be analyzed for BMS-986165 and BMT-153261 by a validated assay. Pharmacokinetic samples collected from subjects who receive placebo will not be analyzed. Individual subject PK parameter values will be derived by noncompartmental methods by a validated PK analysis program. Actual times will be used for the analyses. In addition, plasma samples will be archived for potential metabolites analysis, if the need arises and to the extent possible. Detailed instructions for PK blood collection, labeling, processing, storage, and shipping will be provided to the site in the Study Reference Manual.

The PK parameters to be assessed include:

| | |
|---------------------|---|
| C _{max} | Maximum observed plasma concentration |
| T _{max} | Time of maximum observed plasma concentration |
| C _{trough} | Trough observed plasma concentration |

The area under the concentration-time curve in one dosing interval (AUC[TAU]) will be calculated if possible.

8.6.1 Sampling Schedule

The sampling schedule for the assessment of PK and PD is provided in Table 7. Predose samples must be drawn before the dose on all visit days, and after a fast (for Day 1 and Day 85 visits) of at least 10 hours. As described in Section 1.3, the timing of other procedures at a given visit can be adjusted so that PK sampling can be performed at the scheduled time. If possible, PK samples should be collected for subjects who discontinue treatment due to an AE. Further details of blood collection and processing are provided to sites in the Study Reference Manual.

Table 7: PK and PD Sampling Schedule for BMS-986165 and BMT-153261

| Study Day of Sample Collection | Event | Time (Relative To Dose) Hour: Min | Blood Sample for PK | Blood Sample for IRG | Notes |
|--------------------------------|---------|--------------------------------------|---------------------|----------------------|--|
| 1 | predose | 00:00 | X | X | Samples will be collected after the subject has been fasted for ≥ 10 hours (fasting is required for other assessments at this visit as well). However, subjects may eat after the Hour 2 sample has been collected. |
| 1 | | 00:30 | X | | |
| 1 | | 02:00 | X | | |
| 15 | predose | 00:00 | X | X | |
| 29 | predose | 00:00 | X | X | |
| 57 | predose | 00:00 | X | X | |
| 85 | predose | 00:00 | X | X | Samples will be collected after the subject has been fasted for ≥ 10 hours (fasting is required for other assessments at this visit as well). However, subjects may eat after the Hour 4 sample has been collected. |
| 85 | | 00:30 | X | | |
| 85 | | 02:00 | X | X | |
| 85 | | 04:00 | X | X | |
| 85 | | 06:00 | X | X | |
| 113 | predose | 00:00 | | X | |
| 141 | predose | 00:00 | | X | |
| 169 | predose | 00:00 | X | X | |
| 197 | predose | 00:00 | | X | |
| 225 | predose | 00:00 | X | X | An aliquot of collected blood sample will be included for potential measurement of concomitant medication. |
| 253 | predose | 00:00 | | X | |
| 281 | predose | 00:00 | | X | |
| 309 | predose | 00:00 | | X | |
| 337 | predose | 00:00 | X | X | |

IRG = interferon-regulated gene; PD = pharmacodynamic(s); PK = pharmacokinetic(s)

Note: Predose samples must be drawn before the morning dose of study treatment on the visit day, ie, study treatment will be taken at the site on those days.

8.6.2 Sampling Windows

It is expected that every effort is made to collect PK samples at the times indicated. However, for flexibility in PK sampling, the following windows serve as a guideline for PK sample collection:

- Predose samples must be drawn before the morning dose on the visit day.
- The following windows apply to other samples:
 - ± 0.25 hour for the 0.5-hour sample
 - ± 0.5 hour for the 2-hour sample
 - ± 1 hour for the 4- and 6-hour samples

All samples should be collected using the timepoint labels provided even if they are outside of the suggested window. Actual sample times must be recorded. If samples cannot be taken within the specified time window every effort should be made to take a sample as soon as possible. Deviations from the sampling windows must be noted in the source documents.

Pharmacodynamic sampling will follow the same time window as PK and will be collected at matched PK timepoints.

8.7 Supplemental Assessments: Photography

Sites will be equipped with clinical photography supplies. [REDACTED] will use the photographs to assist in establishing appropriate use of the CLASI instrument for selected visits. Additionally, the photographs will be used to help distinguish a rash related to SLE from a rash arising as a side effect of the study treatment. Any photographs may be used as supplemental documentation for publications and to increase understanding of cutaneous manifestations of interest. Appropriate measures will be applied to ensure subject privacy. Details of study photography are provided in the Central Photography Manual. Only subjects who consented to photography will be photographed.

8.8 Pharmacogenomics

Not applicable

8.9 Biomarkers

Details of blood and urine collection and processing will be provided to the site in the Study Reference Manual. Biomarker samples will generally be collected from all study subjects (with the exception of Day 2 or 3 samples). Blood and urine will be collected at the timepoints shown in [Section 1.3](#) and in [Table 7](#).

The biomarkers to be assessed currently have no utility for clinical decision making, thus, the results for individual subjects will not be shared with either the investigator or the subject; however, the aggregated results may be shared. The aggregated results may be published to further the understanding of BMS-986165 or lupus; however, individually identifiable patient data will not. The end of the study for biomarker samples is defined as up to the maximum allowed in the individual ICF documents. Although the analysis of some biomarkers will be performed immediately, additional biomarker analysis may be delayed while the initial analysis of the study results are interpreted and integrated.

8.9.1 Predictors of Response

Blood will be collected at the screening visit to assess the level of activity of the Type I IFN pathway by measuring the expression of IRGs. In addition, steroid-regulated genes and other gene signatures may be assessed. These biomarkers will be used to test for potential differences in subjects' response to BMS-986165 and CS treatment.

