| 
Pharmacodynamics
 
 To assess the effect of BMS-986165 on PD markers (Section 8.9.2) | 
 Change in mean and median interferon-regulated gene (IRG) expression levels compared to baseline over time and at Week 32 Change in mean complement (C3, C4) and anti-double-stranded DNA (dsDNA) levels compared to baseline over time and at Week 32 Assess the effect of BMS-986165 on measures of global SLE clinical response in subjects based on IRG status (ie, high versus low IRG signature) at Week 32 |

Table 4: Objectives and Endpoints

| Objectives | Endpoints |
|------------|-----------|
| | |
| | |

Table 4: Objectives and Endpoints

| Objectives | Endpoints |
|------------|-----------|
| | |

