11.7.4 Subgroup Analysis

[figure not shown]
Subgroup analyses will be performed for the primary endpoint, SRI(4) response at Week 32. Due to the reduced sample size within subgroup, no model-based adjusted odds ratios will be calculated. These analyses will include point estimates for response rate with asymptotic confidence intervals and the estimated unadjusted difference between study drug and placebo groups with Newcombe 95% confidence limits. P-values will not be reported for subgroup analyses. The following subgroups will be considered:

- Baseline CS dose (< 10 mg/day, ≥ 10 mg/day)
- Baseline SLEDAI-2K Score (< 10 , ≥ 10)
- Geographic region (North America, South America, Japan, rest of world)
- Country
- Gender (male, female)
- Age group (18 - <45 , 45 - <65 , ≥ 65 years)
- Weight ($<$ median weight, \geq median weight)
- BMI (≤ 30 kg/m², > 30 kg/m²)
- Race
- Ethnicity (Hispanic or Latino, not Hispanic or Latino)
- CS Use at baseline (yes, no)
- Anti-malarial Use at baseline (yes, no)
- Immunosuppressant Use at baseline (yes, no)
- Interferon (IFN) status (high, low)
- Years since initial diagnosis (<3 yrs, 3-6 yrs, >6 years)

[figure not shown]
Sponsor: Bristol-Myers Squibb

Protocol no: IM011021

[figure not shown]
Sponsor: Bristol-Myers Squibb

Protocol no: IM011021

[figure not shown]
Sponsor: Bristol-Myers Squibb

Protocol no: IM011021

[figure not shown]

Sponsor: Bristol-Myers Squibb

Protocol no: IM011021

Sponsor: Bristol-Myers Squibb
Protocol no: IM011021

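### The protocol promises a test of differential response by interferon-gene status, but the readable SAP plans no high-versus-low estimate; one exploratory contrast would supply it

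*Protocol*

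**What the plan says.** Protocol 8.9.1, on predictors of response, covers the interferon-regulated genes and other signatures measured at screening and states: "These biomarkers will be used to test for potential differences in" how subjects respond to the study drug and to corticosteroids. In Protocol Table 4, under pharmacodynamics, one Week 32 endpoint is to "Assess the effect of BMS-986165 on measures of global SLE clinical response in subjects based on IRG status (ie, high versus low IRG signature"). Protocol 9.3.3.2 calls the pharmacodynamic evaluation a secondary endpoint.

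SAP 11.7.4 lists 15 subgroup factors for Week 32 SRI(4). One of them is "Interferon (IFN) status (high, low"). For each level the output is a response rate with an asymptotic interval and the "estimated unadjusted difference between study drug and placebo groups with Newcombe 95% confidence limits". The section also says that "no model-based adjusted odds ratios will be calculated", citing the smaller numbers within subgroups, and that "P-values will not be reported for subgroup analyses".

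SAP 13.0 assigns IFN status from screening samples. It adds descriptive biomarker summaries by IFN status within arm, and demographics by IFN status. No readable passage in either document estimates the difference in treatment effect between IFN-high and IFN-low.

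**The concern.** Whether response depends on a marker is a question about the difference between two treatment effects. The planned output gives each effect on its own. A reader who wants the answer that 8.9.1 promises is left to compare the two intervals, and the natural shortcut is to see which one excludes zero. That shortcut is not a test of a difference. The two levels will probably be of unequal size, so the larger one can clear zero and the smaller one fail to, even when the effect is the same in both.

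IFN status is not just another factor on the list. It is the one the protocol names as a predictor to be tested, and inhibition of Type I interferon signalling is part of the study rationale. An apparent effect in IFN-high subjects only could influence whom later trials enrol.

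**Working it through.** **The plan's own figure.** The documents state no power or precision for the IFN analysis, so there is no figure to reproduce on this point. The stated 84% power concerns the whole-arm comparison. It gives the two inputs used here: about 90 subjects per arm and a 20-point difference (SAP 5.1).

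**Assumptions not in the documents.** Placebo SRI(4) rate 30–40%; IFN-high share 60–80%, equal across arms.

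**Step 1: how often separate intervals disagree under a uniform effect.** Within each level, enumerate all binomial outcomes for one active arm and placebo, form the Newcombe 95% interval, and add up the probability that it lies above zero. Call this P_H in IFN-high and P_L in IFN-low. The levels are independent, so

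- P(high only) = P_H × (1 − P_L)
- P(low only) = P_L × (1 − P_H)

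At a 70% share (63 high and 27 low per arm), with placebo 30% and active 50% in both levels, P_H = 0.654 and P_L = 0.334. High only is 0.654 × 0.666 = 0.436. Low only is 0.334 × 0.346 = 0.116.

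Over placebo rates of 30–40%, with a true 20-point effect in both levels:

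| IFN-high share (high/low per arm) | High only | Low only |
|---|---|---|
| 60% (54/36) | 33–34% | 17–18% |
| 70% (63/27) | 44–46% | 10–12% |
| 80% (72/18) | 51–52% | 8% |

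SAP 11.7.1 specifies the continuity-corrected Newcombe interval; 11.7.4 does not say which form it uses. The table is uncorrected. With the correction the ranges are 33–54% for high only and 6–18% for low only, so the picture is the same.

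**Step 2: dependence on the true effect.** With a uniform 10-point effect, high only falls to about 15–21%. With no effect in either level it is about 2–3% per regimen.

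**Step 3: precision of the direct contrast.** The quantity is D = (risk difference in IFN-high) − (risk difference in IFN-low), and its variance is the sum of the two variances. At 63/27 with rates 0.4 and 0.6, each arm contributes 0.24/n:

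- One regimen: 1.96 × √(0.48/63 + 0.48/27) = 1.96 × 0.159 = 0.31, or ±31 points.
- Three active arms pooled: 1.96 × √(0.24/189 + 0.24/63 + 0.24/81 + 0.24/27) = 1.96 × 0.130 = 0.255, or about ±26 points.

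**Step 4: power of the contrast.** For a true 20-point high-low difference (20 points in IFN-high, none in IFN-low) at 63/27 and placebo 40%, the standard error is again 0.159. Power is about Φ(0.20/0.159 − 1.96) = Φ(−0.70), or 24%. Over IFN-high shares of 50–80% and placebo rates of 30–40% it is 19–30%.

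**The case against.** The strongest points on the other side are these.

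- **The plan makes no interferon-specific claim.** A reader might infer that the sponsor intends to conclude that the drug works in one IFN level whenever that interval alone excludes zero. The documents do not support this. SAP 11.7.4 is descriptive and withholds p-values, and Protocol 8.9 says the biomarkers have no current use in clinical decisions. This stands: misreading is a risk, not a planned conclusion.
- **The information is not lost.** A reader might also infer that the output cannot address the question at all. That goes too far, because the contrast can be derived from the reported rates and subgroup sizes. What is missing is a prespecified estimate with its interval and a statement that it governs interpretation.
- **The protocol wording is loose.** The sentence in 8.9.1 also covers other gene signatures and response to corticosteroids, which are not randomized. The Table 4 item can be met by within-level estimates, and it sits outside the listed secondary efficacy endpoints. This is fair, but 8.9.1 does say test, and the readable SAP has none.
- **Small numbers do matter.** At a 70/30 split, IFN-low supplies 70% of the contrast's variance (0.0178 of 0.0254). A logistic model with the 13-level stratum would need about 20 parameters (1 + 12 + 3 + 1 + 3), and SAP 11.7.1 already allows region to be dropped if the fit is unstable. This bears on the form of the fix. It is not a reason to omit a simple contrast.
- **Absence cannot be proved.** Neighbouring efficacy text is redacted, and SAP 5.5 refers to a section 11.7.5 that cannot be read. The point is therefore limited to readable text. Section 11.7.4 itself is readable, and its exclusions cover IFN status.

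**Conclusion.** The point holds as a cheap improvement. The protocol promises a test of differential response by interferon-gene status, and the readable SAP yields no estimate of the high-versus-low difference. Under a uniform 20-point effect, exactly one of the two intervals excludes zero in about half or more of trials for a given regimen: at 60/40, roughly 33% + 18% = 51%; at 80/20, roughly 51% + 8% = 59%. The size depends on the assumed IFN split and placebo rate and, above all, on the true effect, since the disagreement shrinks sharply as that effect falls. Nothing here touches the primary analysis, its error control or safety. Nor would the added contrast settle the question: with 19–30% power per regimen it guards against over-reading but could not confirm a plausible interaction.

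**What to change.** In SAP 11.7.4, for IFN status only:

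1. Add the IFN-high minus IFN-low difference of the Week 32 SRI(4) risk differences (nonresponder-imputed) with a 95% CI, for each regimen and for pooled active arms versus placebo, labelled exploratory.
2. Optionally add a logistic model with a treatment-by-IFN term, using the reduced five-level stratum that SAP 11.7.1 already defines as its fallback. That needs 1 + 4 + 3 + 1 + 3 = 12 parameters.
3. State that any statement of IFN-dependent response rests on this contrast, and that a CI including zero does not show absence of IFN dependence.

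If the sponsor prefers not to add it, Protocol 8.9.1 should be reworded as descriptive so that the two documents agree.

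The cost is a few lines of SAP text and one table, with no new data: IFN status comes from the screening sample, which Protocol Table 1 requires for study entry. The downside is a wide interval, which needs the wording in item 3 so that it is not taken as evidence of no difference.
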